6.3 Exclusion Criteria

1. current use, or use within the previous month*, of medical therapy for incontinence or weight loss
2. pregnant or gave birth in the previous 6 months
3. urinary tract infection (dipstick urinalysis positive for leukocyte esterase, nitrites or blood) or report having ≥ 4 urinary tract infections in the preceding year
4. incontinence of neurologic or functional origin (by history)
5. report prior anti-incontinence or urethral surgery, pelvic cancer or pelvic irradiation
6. report significant medical conditions of the genitourinary tract (genitourinary fistula, interstitial cystitis, symptomatic pelvic organ prolapse)
7. report a medical condition that would affect the safety and/or efficacy of a weight management program involving diet and physical activity, including type 2 diabetes requiring medical therapy that may cause hypoglycemia, chronic steroid use or uncontrolled hypertension (systolic blood pressure >180 mm Hg or diastolic blood pressure > 100 mm Hg); women with a history of coronary heart disease may participate with written approval from their primary care physician
8. engaged in an active weight loss program and/or experienced a weight reduction of 10 lbs or more in the past 3 months
9. report conditions that, in the judgment of the clinical center Principal Investigator, render potential participants unlikely to follow the protocol for 18 months, including illness likely to be terminal within 2 years, plans to move, substance abuse, significant psychiatric problems, or dementia
10. participating in another research study that involves investigational drugs or can potentially confound the results of PRIDE

* Potential participants may be re-screened one month after stopping medical therapy for incontinence or obesity. Prior medical therapy for incontinence or obesity will not affect eligibility but participants will be asked not to initiate any

treatment for incontinence or obesity during the study period except as directed by the study protocol.

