4.3.3 Randomization Visit

The Randomization Visit (RV) must be completed within 9 months of the Eligibility Screening interview. If a participant cannot complete the RV within 9 months of the Eligibility Screening interview she must be eliminated from the screening process, but may be re-screened with a new ID number at a later date. If the RV is performed more than 3 months after Screening Visit 1 certain eligibility criteria must be re-checked. Please refer to the Guidelines for Delayed Screening Schedules, Ch. 9, Appendix 9G.

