8.3 SOURCE OF MEDICAL CARE

Having PRIDE staff participate in the medical care of study participants could lead to differential treatment of participants in the two arms of the study and affect the outcomes under investigation. Thus, each candidate must have a health care provider outside of PRIDE who will provide primary care. Any candidate with coronary heart disease must have a letter of approval from her health care provider before enrolling in PRIDE to ensure that she can safely engage in the diet and exercise program. If a candidate does not have a source of medical care outside of PRIDE, study staff should help the candidate identify a provider.

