8.7.22 Question 20a - d

Read question 20 to the candidate and then read each of the medical conditions/procedures in questions 20a, 20b, 20c and 20d. Fill in the bubble "yes" or "no" for each item. If the candidate reports "chest pain" or "difficulty breathing" ask if she has seen a doctor for her symptoms. Probe to determine the correct diagnosis. If this is unclear, consult the Principal Investigator or Coordinating Center for direction. If any of the responses are marked "yes", continue to question 20e.

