8.7.23 Question 20e

Candidates with coronary heart disease must have permission from a cardiologist or primary care physician to participate in PRIDE. Even though the exercise program is not considered strenuous, the candidate may have been sedentary for a long time and caution is prudent. Ask the candidate if she is willing to obtain written approval from a medical professional to participate in the study. If she says "yes", she is eligible to continue screening. You can offer to send study information and a form for her doctor to sign and fax to the

PRIDE site. Make a note on the tracking log that a letter is expected prior to Randomization. Candidates currently enrolled in Cardiac Rehabilitation programs must finish these before being screened for PRIDE. Continue to question 21.

8.7.24 Question 21

If the candidate is a diabetic fill in the bubble “yes” for question 21 and proceed to answer question 21 a, and, if applicable, question 21 b and/or 21c. If the candidate is not a diabetic or doesn’t know, fill in the appropriate bubble and skip to question 22.

Please note: if the response to question 21a is “Don’t Know” be sure to flag the candidate for further follow-up. Insulin-dependent diabetics and diabetics on some oral medications are not eligible for the study. The method of treating their diabetes must be clarified before randomization can occur.

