Appendix 9B

Guidelines for Delayed Screening Schedules in PRIDE

As of October 28, 2004, the maximum allowed interval between the Eligibility Screening interview and the randomization visit has been extended to 9 months. There will be no restrictions on the intervals between the Eligibility Screening, OV, SV1, SV2 and RV. These changes facilitate the accumulation of groups for intervention sessions. The extension of screening time does not change the entry criteria for the study. Eligibility criteria should be reviewed periodically as follows:

- A. If the interval between Eligibility Screening(ES) and Orientation Visit (no other forms completed) is more than 3 months, all questions on the Eligibility Screening Form (ESF) must be reviewed with the candidate before proceeding with further visits. The interviewer should post queries for the ESF and update Q.30 as necessary.
- B. If the candidate has completed one or more screening visit forms (apart from the ESF) AND the duration between Screening Visit 1 and Randomization Visit is more than 3 months, the following items must be rechecked:

Check if done:	Recheck:	Form:	Action:
	Body Mass Index (BMI)	Review Eligibility Screening Form (ESF) Question 10 with the candidate.	If Height and Weight form was already completed AND the candidate's BMI is now out of range, she is still eligible. Continue with screening. If Height and Weight form was not completed AND the candidate's BMI is now out of range, she is not eligible. Complete the Inclusion/Exclusion Form and mark "No" for criteria 1B.
	Weight loss of 10 pounds or more	Review ESF Question 11 with the candidate.	If candidate has lost 10 pounds or more in the last 3 months, she is not eligible. Complete the Inclusion/Exclusion Form and mark "Yes" for exclusion criteria 2B.
	Weight loss	Review ESF	If candidate has started a weight loss

	program	Question 16 with the candidate.	
program AND is willing to stop, no action is needed.
 
If candidate has started a weight loss program AND is not willing to stop, complete the Inclusion/Exclusion Form and mark "Yes" for exclusion criteria 2B.

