	Medications	Review ESF Question 17 with the candidate to check for new medications.	
If candidate has started a weight loss or incontinence medication AND is willing to stop, no action is needed.
 
If candidate has started a weight loss or incontinence medication AND is not willing to stop, complete the Inclusion/Exclusion Form and mark "Yes" for exclusion criteria 2A.
 
If the Medications Form was completed and the candidate has new medications, the Medications Form should be updated by posting a query.

	New diagnosis or medical condition	Review ESF Questions 8, 15, 19, 21-26 and Health History Form Questions 16a-16g with the candidate.	
If the candidate is not eligible, do not post queries to the ESF or Health History Form.
 
Complete the Inclusion/Exclusion Form as follows:
 
If candidate is not eligible because of:
 
ESF Q.8 ☉ mark "Yes" for exclusion criteria 2C.
 
ESF Q.15 ☉ refer candidate for treatment. She is eligible to continue screening after treatment.
 
ESF Q. 19 ☉ mark "Yes" for exclusion criteria 2F.
 
ESF Q. 21 ☉ mark "Yes" for exclusion criteria 2H.
 
ESF Q. 22 ☉ mark "Yes" for exclusion criteria 2H.

			
ESF Q. 23 ☉ mark "Yes" for exclusion criteria 2H.
 
ESF Q. 24 ☉ mark "No" for inclusion criteria 1J.
 
ESF Q. 25 ☉ mark "No" for inclusion criteria 1J.
 
ESF Q. 26 ☉ mark "Yes" for exclusion criteria 2I.
 
HHx Q.16a-16g☉ mark "Yes" for exclusion criteria 2E.

	Participation in a research study	Review ESF Question 28 with the candidate.	If the candidate is not eligible, complete the Inclusion/Exclusion Form and mark "Yes" for exclusion criteria 2J.

CHAPTER 10

SCREENING VISITS

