In this case, mark the Inclusion/Exclusion form as follows: If the participant responds “Yes” to 16a, 16b, 16c, or 16d, then mark “Yes” for Exclusion Criteria, item G. If the participant responds “Yes” to 16e, 16f or 16g, then mark “Yes” for Exclusion Criteria, item E. If the participant marks “don’t know” to any of the questions 16a to 16g she is still eligible to continue screening.

Questions 17. This question probes for a history of hypertension. A “yes” response does not exclude the participant. Blood pressure will be measured during screening to determine eligibility.

Question 18. High cholesterol does not exclude the participant.

Question 19. If the participant has a history of coronary heart disease she is not excluded from PRIDE, but she must obtain approval from her health care provider in order to participate in PRIDE. Please confirm that she has obtained a letter and make sure the letter is filed in her study binder prior to the Randomization Visit.

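### For women randomised more than 3 months after Screening Visit 1, the Appendix 9B re-check omits both coronary heart disease questions (ESF 20 and Health History 19)

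*Protocol*

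**What the plan says.** Protocol section 6.3, exclusion 7 (current amended text), makes coronary disease a conditional entry: "women with a history of coronary heart disease may participate with written approval from their primary care physician". The operations manual repeats the condition three times:

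- Section 8.3: "Any candidate with coronary heart disease must have a letter of approval from her health care provider before enrolling in PRIDE".
- Section 8.7.23 (ESF 20e): "Candidates with coronary heart disease must have permission from a cardiologist or primary care physician to participate in PRIDE". The same section says that a candidate in a cardiac rehabilitation programme has to complete it before she is screened.
- Section 10.3.6.1 (Health History 19): "she is not excluded from PRIDE, but she must obtain approval from her health care provider in order to participate in PRIDE". The letter is to be in her binder before the RV.

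On delayed screening, section 4.3.3 states: "If the RV is performed more than 3 months after Screening Visit 1 certain eligibility criteria must be re-checked". Appendix 9B adds that "The extension of screening time does not change the entry criteria for the study". Item B of that appendix then sets out the re-check row by row. The row headed *New diagnosis or medical condition* names ESF "Questions 8, 15, 19, 21-26 and" Health History 16a to 16g, and its action column covers those same questions.

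**The concern.** The row exists to catch conditions that have arisen while a woman waits for her group to form. Within the run ESF 19 to 26 it skips only question 20. Both places where the screening forms ask about coronary disease, ESF 20 and Health History 19, are therefore missing from the one step designed to update them.

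What is at stake is the approval letter. It is required so that women with coronary disease can take part safely in a diet and exercise programme, and two-thirds of women are allocated to that programme. A woman found afterwards to have been randomised in error stays in the study (section 12.4), so the check has to come before randomisation.

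**Working it through.** The check compares texts, because the plan gives no figure to reproduce.

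**1. What item B re-asks.** By row:

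| Row | Questions |
|---|---|
| Body mass index | ESF 10 |
| Weight loss of 10 lb or more | ESF 11 |
| Weight loss programme | ESF 16 |
| Medications | ESF 17 |
| New diagnosis or medical condition | ESF 8, 15, 19, 21, 22, 23, 24, 25, 26; Health History 16a–16g |
| Other research study | ESF 28 |

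That is 14 ESF questions. Of the eight questions ESF 19 to 26, seven are re-asked and 20 is not. Health History 19 is not re-asked.

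**2. Does conditional entry explain the omission?** No. ESF 15 is in the same row and leads only to treatment, after which screening continues. ESF 16 and 17 are re-checked although a woman willing to stop may go on.

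**3. Is the delay covered elsewhere?** Delays before the Orientation Visit (Appendix 9B item A) or before SV1 (section 9.4.1) trigger a review of the ESF as a whole, so ESF 20 is covered there. A delay after SV1 has only item B.

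**4. What else could find a new coronary diagnosis before randomisation?**

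- *Criteria review at the RV* (protocol 8.3.4, manual 12.3.6). It covers every criterion, including exclusion 7. The working checklist, Appendix 12A exclusion H, names neither coronary disease nor the letter, and it is sourced to forms filled in earlier.
- *Medication questions.* These come in the item B medications row, at Screening Visit 2 (SV2; section 10.4.2.3) and at the RV (section 12.3.6). A new cardiac drug could be noticed. Staff are not told to ask about heart disease, and the exclusionary classes are steroids, weight loss, diabetes and incontinence drugs.
- *ESF 24 and 25*, in the same row. They re-ask about walking two blocks without stopping or an aid, which bears on exertional limitation but not on diagnosis.
- *Health History at SV2.* The protocol schedule (8.1) allows it at either screening visit, and section 10.6 places the RV within 4 weeks of SV2, so it could be recent. But the manual puts it in the SV1 procedures (10.3.6), and section 4.3 and Appendix 9B remove interval limits between these visits.
- *Interventionist interview at SV2* (10.4.2.2). It is about likely adherence.
- *Physician consent* (protocol 8.1, SV1 or SV2). A consent given earlier would not reveal a later diagnosis.

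**5. Scale, as illustration only.** The documents give neither the number delayed nor a rate of new coronary disease. Assume 10–30% of the 330 women are delayed, 0.2–1% are newly diagnosed per year, and the delay is 0.25–0.75 years. The upper end is generous, since the 9-month limit runs from the earlier eligibility interview.

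- New diagnoses, low: 330 × 0.10 × 0.002 × 0.25 = 0.0165. High: 330 × 0.30 × 0.01 × 0.75 = 0.7425.
- Missed, if the other checks catch 90% (low case) or 50% (high case): 0.0165 × 0.10 = 0.00165; 0.7425 × 0.50 = 0.371.
- Of these, allocated to weight loss (× 2/3): 0.0011 to 0.248.

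**The case against.** The strongest reply is that the entry rule is still enforced at the RV. Staff must confirm that every criterion is met, and exclusion 7 names both the disease and the approval. Section 4.3.3 also says openly that only certain criteria are re-checked. Appendix 9B leaves out other items too (ESF 14, ESF 18 and Health History 17), and most actions in the row record ineligibility, which coronary disease with approval is not. The programme is mostly unsupervised walking, starting at 50 minutes a week and tailored to fitness and safety (16.3.5).

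Much of this stands. It means that no statement in the documents is false and that the exposure is small. It does not supply a question about coronary disease at the point where new conditions are meant to be asked about.

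Two stronger readings might be inferred and are not supported:

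- *That hypertension, also left out of the row, is safely re-measured at the RV while coronary disease is not.* The documents disagree on whether blood pressure is taken there. Section 14.2.1 and the Appendix 10C note to question 17 say or imply that it is. The protocol schedule (8.1) shows none at the RV, the visit map (Appendix 4A) marks it optional, and the RV forms list (12.2) omits it. It is not a firm contrast.
- *That a scripted chest-pain question is lost.* Section 8.7.22 tells staff what to do if a candidate reports such symptoms ("ask if she has seen a doctor for her symptoms"). The wording of ESF 20a–d is not shown, so how much symptom screening is lost cannot be judged.

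**Conclusion.** The point holds as a minor safety and eligibility correction. For women randomised more than 3 months after SV1, a coronary diagnosis made after the ESF and Health History were completed is not specifically re-asked. Finding it depends on the general criteria review, a new drug being noticed, the walking items, or the woman mentioning it.

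A reader might infer that such women would be randomised without approval. The documents do not support that: several general checks remain, and the illustration stays below one woman throughout. That illustration rests wholly on assumed inputs and is no estimate for this trial. The omission itself is certain from the text. No endpoint, analysis or power calculation is touched.

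**What to change.** Change the row to: *ESF Questions 8, 15, 19–26 and Health History Questions 16a–16g and 19.* Add one action line: *If newly Yes to ESF 20 or Health History 19, she is not excluded, but written physician approval must be on file, and any cardiac rehabilitation programme completed (8.7.23), before randomization.*

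The rehabilitation clause is needed because a letter alone would not satisfy section 8.7.23. The change applies existing rules and adds no criterion. It costs two more questions in a re-check that already takes place, and an occasional delay to randomisation while a letter is obtained or a rehabilitation programme ends.

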10.0 SCREENING VISITS

10.1 OVERVIEW

Two Screening Visits will be completed prior to the Randomization Visit. The visits have been designed to provide as much flexibility as possible for investigators and participants. Most questionnaires are self-administered forms that can be completed at home or in clinic, and most forms or procedures can be done at either of the two screening visits. There are no specified intervals between these visits.

10.2 PURPOSE OF THE SCREENING VISITS

The Screening Visits are used to establish eligibility for the study and to collect baseline information that will be used to test the trial's hypotheses.

10.3 SCREENING VISIT 1 (SV1)

10.3.1 Preparation for SV1

SV1 is the participant's first individual clinic visit. Call to remind her about the appointment time, length of time it will take and to bring with her the take-home forms and diary she was given at the Orientation Visit. Print out the SV1 data forms from the PRIDE website. (Any form or questionnaire with "SV" as a visit box choice can be done at either SV1 or SV2.) **The forms followed by an asterisk in the box below are used to collect information that is critical for participant eligibility.**

Forms/Logs needed during Screening Visit 1:

- Screening Visit Checklist (to be updated)
- Informed Consent/HIPPA (if not signed at OV)
- 7-day Voiding Diary #1 (if not presented at OV)
- 7-day Voiding Diary Data Entry Form* (SV)
- Vital Signs*
- Height and Weight*
- Health History Form*
- Dipstick Urine Analysis*
- 7-day Diet and Exercise Diary
- Paffenbarger Activity Questionnaire (take home)
- Food Frequency Questionnaire (take home)

- Incontinence Impact Questionnaire (take home)
- Urogenital Distress Inventory (take home)
- Health & Activity Form (SF-36) (take home)
- Inclusion/Exclusion Form* (to be updated)
- Participant Tracking Log (to be updated)

In addition to the forms and logs listed above, please have the following available:

- participant's binder with the participant's contact form, the completed Eligibility Screening form, Informed Consent form and HIPPA authorization
- an envelope or folder and PRIDE pen for the take-home questionnaires.

If the participant has not yet signed Informed Consent for PRIDE, she must do so before the SV1 begins (see Chapter 9.4).

10.3.2 SV1 Procedures

10.3.2.1 Review of the Take-Home Questionnaires

Collect and review the Demographics form and the 2IQ to be sure there are no missing values or mistakes. If mistakes were made and corrected, be sure to circle the correct response, initial and date the correction before the form is faxed to the data system.

10.3.2.2 Review of 7-Day Voiding Diary

Certified study staff will review the 7-day Voiding Diary for accuracy and completeness immediately upon receipt at the clinic. Enter the date of today's visit and your Staff ID# on every completed diary page as you review it with the participant. Be sure the participant's ID number/acrostic is entered on every completed page.

If the participant has not filled out the diary correctly or completely for at least 5 of the 7 days, or if she has not had at least 10 episodes of incontinence, **the participant is not eligible** for PRIDE. In this case, you should cancel the remainder of the visit. You may either allow the participant a second chance by giving her another diary and another

SV1 appointment OR complete the Inclusion/Exclusion Checklist marking “no” for Inclusion Criteria, item I.

Ideally, the diary should reflect 7 consecutive days of the participant’s experience. However, **gaps in recording days** are admissible up to a limit of two weeks. If the participant forgets to record for a day, or fails to record days due to extenuating circumstances (e.g. a family emergency), she should continue the diary as soon as possible, entering the correct day and date at the start of the page. If the gap in recording is 14 days or more the diary is inadmissible. If the participant had a legitimate and unique problem that led to the interruption she should be instructed to start a new diary and the visit should be re-scheduled. If the participant simply forgot or was unreliable at documenting her experience, she is not eligible for PRIDE. In this case, complete the Inclusion/Exclusion data form, marking “no” for Inclusion Criteria, Item I.

The completed 7-day Voiding Diary should be kept with the participant’s file at the clinical site. The Diary is not sent to the Coordinating Center unless requested.

Reviewer Instructions for reviewing the Diary:

1. Discuss the diary entries with the participant. If the diary is incomplete, probe the participant to complete as much missing data as possible.

For *each diary day*, the participant should have entered the:

- a. Day of the week and date
- b. Time she got up for the day (AM or PM)
- c. Time she went to bed for the night (AM or PM)
- d. Degree to which she recorded all episodes for the day
- e. Time each episode and whether AM or PM
- f. Urinations in toilet
- g. Leakages, and if she did leak, the reason for leakage
- h. What she was doing when she leaked

For each entry to be considered complete the participant must have a check in both column 2 (Did you urinate in the toilet? No or Yes) and column 3 (Did you leak urine? No or Yes) and each “Yes” check in

column 3 (Did you leak urine?) must be accompanied by one check in column 3a (Reason for Leakage). The participant should decide which of the three categories best describes her episode of urinary incontinence.

Examples of Mistakes on the Diary

A.

1. TIME	2. DID YOU URINATE IN THE TOILET?	3. DID YOU LEAK URINE?	IF YES ⇒	3a. REASON FOR LEAKAGE Please check only one main reason
7:30  AM  PM	 No  Yes	 No  Yes	⇒	 Urge  Stress  Other

- Participant did not check No or Yes in column 3. Query the participant and have her check the appropriate response.

B.

1. TIME	2. DID YOU URINATE IN THE TOILET?	3. DID YOU LEAK URINE?	IF YES ⇒	3a. REASON FOR LEAKAGE Please check only one main reason
12:15  AM  PM	 No  Yes	 No  Yes	⇒	 Urge  Stress  Other

- Participant did not check AM or PM in column 1. Query the participant (you can note the order of the entry in this day’s diary) and have her check the correct response.
- Participant did not check No or Yes in column 2. Query the participant and have her check the appropriate response.

C.

1. TIME	2. DID YOU URINATE IN THE TOILET?	3. DID YOU LEAK URINE?	IF YES ⇒	3a. REASON FOR LEAKAGE Please check only one main reason
6:10  AM  PM	 No  Yes	 No  Yes	⇒	 Urge  Stress  Other

- Participant checked Yes in column 3 (Did you leak urine?) but did not make a corresponding check in column 3a (Reason for Leakage).

- Query the participant. Review time of entry and other responses to assist in recall of circumstances surrounding the event.
- **Reviewer:** “On day 3 at 6:10 PM you have recorded that you urinated in the toilet and you leaked, but you did not record the reason for leakage. Could you think back to this time? Try to recall what caused this leak and check the reason in column 3a.”
2. Check to determine if the participant used the “Extra Entries” Page at the end of the diary. If the extra page was used, make sure that the participant entered the **date** of each episode in the left-most column.
 3. Review the entries for what the participant was doing when she leaked. In particular, review what she was doing when she marked “Other” in column 3a, to confirm that these cannot be classified as “Urge” or “Stress” episodes. One example of “Other” might be “vaginal voiding”. This occurs more often in very obese people with folds of thigh fat. Leakage may occur when the participant is sitting but is not noticed until she stands up.

Please review Chapter 8. 7. 13 for more typical scenarios of incontinence. If you are in doubt about how an episode of incontinence should be classified, please consult your site urogynecologist or call the Coordinating Center for guidance.

4. The reviewer should divide the diary into “**daytime**” and “**nighttime**” by drawing a line after the last void before the participant went to bed for the night. (“Nighttime” is based on the participant’s bedtime). **Note:** If a diary entry was made at the same time as the participant’s bedtime, the entry should be included in the “**daytime**” urinations category. In some cases participants have unusual schedules with no regular bedtime or wake-up times. In such a case, you do not have to draw a line; simply count all “sleeping” episodes as nighttime and all “awake” episodes as daytime.
5. Add up the number of ‘checked’ boxes in columns 2, 3 and 3a to obtain the total number of urinations in the toilet, the total number of leakages, the total number of “Urge” episodes, the total number of “Stress episodes and the total number of “Other” episodes. This is a very important step – please recheck your additions when you have finished. Enter the totals in the appropriate shaded boxes at the

bottom of each diary page. **The totals for the daytime and nighttime episodes should be added and recorded separately.** If the participant completes multiple pages on any day, add the totals on all pages together for that day. **For each column there is a “Daytime” and “Nighttime” total.** Do not add “No” responses to the total. The 5 columns include:

1. Did you urinate in the toilet?	Total number of Daytime “Yes” responses only Total number of Nighttime “Yes” responses only
2. Did you leak urine?	Total number of Daytime “Yes” responses only Total number of Nighttime “Yes” responses only
3. Reason for leakage: Urge?	Total number of Daytime “Urge” responses Total number of Nighttime “Urge” responses
4. Reason for leakage: Stress?	Total number of Daytime “Stress” responses Total number of Nighttime “Stress” responses
5. Reason for Leakage: Other?	Total number of Daytime “Other” responses Total number of Nighttime “Other” responses

